The changes described in this amended protocol require IRB/IEC approval prior to implementation.

The changes herein affect the Informed Consent. Sites are required to update and submit for approval a revised Informed Consent that takes into account the changes described in this protocol amendment.

Amendment 01

Amendment rationale

With this amendment, in order to clarify the main objective of this study, the previous secondary objective “To collect long-term data on serious adverse events and adverse events of special interest” has been elevated to primary objective. In addition, the protocol has been amended to clarify the safety monitoring guidance and to include the collection of all AEs (including non-serious AEs) and an investigator attestation of continued clinical benefit.

The study continues to allow continued access to pasireotide for patients treated with the compound in previous Novartis sponsored studies for as long as they benefit from it. This roll-over study has been opened since 10-Jun-2013 currently with a total of 95 patients enrolled and 80 patients ongoing.

Changes to the protocol

Changes to specific sections of the protocol are shown in the track changes version of the protocol using strike through red font for deletions and red underlined for insertions.

The following changes have been implemented:

The Protocol summary is also updated correspondingly

Section 2.1: Update to the study rationale to include the primary endpoint to evaluate long term safety date.

Section 2.6: The inclusion of the Risk-Benefit section

Table 3-1: Updated with revised study objectives and endpoints. The primary objective is to evaluate long term safety data. The secondary objective is to evaluate clinical benefit as assessed by the investigator.

Section 4.1: Updated to clarify that all adverse events and serious adverse events will be collected continuously throughout the study and to specify that at every visit, the investigator is required to confirm that the patient continues to have clinical benefit and may continue receiving study treatment.

Section 6.1.5: Updated to specify that at every visit, the investigator is required to confirm that the patient continues to have clinical benefit and may continue receiving study treatment

Section 6.2: Revised to refer to Appendices regarding dose modification guidelines

Section 6.5: Clarification of drug labeling process

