2.4 Definition of end of the study

End of study is defined as either 10 years from FPFV (or until 10-Jun-2023 in the UK) or when all patients on this study have permanently discontinued pasireotide treatment or have been able to obtain commercial supply according to local regulations or have been able to receive the drug through country-specific programmes outside of this clinical trial (applicable to Brazil, France, Germany, India, Italy, Malaysia, Mexico, Peru and Thailand) and the end of treatment visit and all safety follow-up procedures have been performed for each patient, whichever comes first.

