4.1 Data analysis general information

The statistical analysis of these data will be performed by IQVIA personnel in accordance with the data analysis section, Section 10, of the study protocol which is available in [Appendix 16.1.1 of the CSR]. Important information is given in the following sections and details are provided, as applicable, in [Appendix 16.1.9 of the CSR].

Data included in the analysis

Final analyses will be performed when all patients have been followed for 3 months (84 days) following the last dose of pasireotide LAR treatment and for 1 month (30 days) following the last dose of pasireotide s.c. treatment.

All events with start date before or on the cut-off date and end date after the cut-off date will be reported as 'continuing at the cut-off date'. The same rule will be applied to events starting before or on the cut-off date and not having documented end date. This approach applies, in particular, to adverse event reports. For these events, the end date will not be imputed and therefore will not appear in the listings.

It is planned that the data from all centers that participate in this trial will be pooled and analyzed. Unless otherwise specified, qualitative data will be described using frequency and percentages, while quantitative data, will be described using descriptive statistics: n, mean, standard deviation, median, minimum, and maximum.

All data will be summarized and listed by indication (acromegaly, Cushing's disease and Others) and formulation (s.c. and LAR).

For the formulation, the variable can be derived from the DAR panel from the DARTYP1C variable, the values captured are 533 and 838 which correspond to Pasireotide LAR and Pasireotide s.c., respectively.

The indication will be derived based upon the parent study number from the HIS panel using the PRVSTY2C variable as described in the following Table 2-1 with the exception of parent study numbers CSOM230C2110E and CSOM230B2219. For those two parent studies, the indication will be derived from the parent study data sets as shown in Table 2-2.

Parent study number	eCRF	Indication	Indication group
CSOM230B2201E	78	Acromegaly	Acromegaly
CSOM230B2208E	79	Cushing's disease	Cushing's disease
CSOM230D2203	81	NET other pituitary and EAS	Other diseases
CSOM230B2305	82	Cushing's disease	Cushing's disease
CSOM230X2203	83	Dumping syndrome	Other diseases
CSOM230C2305	84	Acromegaly	Acromegaly
CSOM230G2304	85	Cushing's disease	Cushing's disease

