CSOM230C1202	86	Acromegaly or pituitary	Acromegaly
CSOM230C2402	87	Acromegaly	Acromegaly
CSOM230X2404	115	Melanoma	Other diseases
CSOM230X2404	116	Melanoma	Other diseases
CSOM230C2413	117	Acromegaly	Acromegaly
CSOM230B2411	125	Cushing's disease	Cushing's disease
CSOM230XDE04	126	Prostate cancer	Other diseases
CSOM230D2401	136	Pituitary adenomas	Other diseases
CSOM230DIC03	137	NET	Other diseases

Table 2-1 Derivation of the indication information – Part 1

Table 2-2Derivation of the indication information – Part 2

Parent study number	eCRF code	Parent data set	Parent data set variable	Indication	Indication group
CSOM230C2110E1 CSOM230C2110E1 CSOM230B2219	80 80 114 or 113	ADMG ADMG AIDENT	CLIND CLIND DISTYP3A	Carcinoid Acromegaly Acromegaly	Other diseases Acromegaly Acromegaly
CSOM230B2219	114 or 113	AIDENT	DISTYP3A	Cushing's disease	Cushing's disease

Treatment period

The overall observation period will be divided into two mutually exclusive segments:

on-treatment period: from day of first dose of study medication in the roll-over study to 3 months (84 days) following the last dose of pasireotide LAR treatment and to 1 month (30 days) following the last dose of pasireotide s.c. treatment.

post-treatment period: starting at 3 months+1 day (day 85) following the last dose of pasireotide LAR treatment and at 1 month+1 day (day 31) following the last dose of pasireotide s.c. treatment.

Safety summaries (tables, figures) include only data from the on-treatment period. In addition, a separate summary for death including on treatment and post treatment deaths will be provided. In particular, summary tables for adverse events (AEs) will summarize only on-treatment events, with a start date during the on-treatment period (treatment-emergent AEs).

However, all safety data (including those from the post-treatment period) will be listed and those collected during the post-treatment period will be flagged.

Study Treatment

Study drug and investigational treatment refer to pasireotide. Patients are to use the study treatment based on the parent protocol.

Date of first/last administration of study drug

The start date of study drug is defined as the first date when a non-zero dose of study drug was administered in the roll-over study and recorded on the Dosage Administration Record (DAR) eCRF.

The date of last administration of study drug is defined as the last date when a non-zero dose of study drug was administered and recorded on DAR eCRF.

Laboratory data

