6.2.2 Safety Set

The Safety Set includes all patients who received at least one dose of study medication (Pasireotide) after enrolling into the roll-over protocol.

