7.1.1 Primary endpoint

The assessment of safety will be based mainly on the frequency and severity of AEs, AESI and SAEs. See also Section 7.4.1.

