7.3 EXTENT OF EXPOSURE

Definitions of duration of exposure, cumulative dose, average daily dose, actual dose intensity (DI), as well as intermediate calculations, include:

Pasireotide s.c.:

- Duration of exposure (days): min(last date of rollover study drug, date of death, date of data cut-off) first date of rollover study drug + 1
- Cumulative dose (μg): total dose of study drug taken by a patient in the rollover study
- Number of dosing days (days): duration of exposure number of zero dose days
- Average daily dose (μg/day): cumulative dose (μg) / number of dosing days (days)
- DI (µg/day): cumulative dose (µg) / duration of exposure (days)

Pasireotide LAR:

- Duration of exposure (months): (min(last date of rollover study drug+27, date of death, date of data cut-off) first date of rollover study drug + 1)/30.4375
- Cumulative dose (mg): total dose of study drug taken by a patient in the rollover study

- Number of dosing months (months): duration of exposure number of zero dose months
- Average monthly dose (mg/month): cumulative dose (mg) / number of dosing months (months)
- DI (mg/month): cumulative dose (mg) / duration of exposure (months)

Duration of exposure to study drug, average daily dose and DI will be summarized descriptively overall and by indication and formulation.

Summary of duration of exposure of study treatment in appropriate time units will include categorical summaries and continuous summaries (i.e. mean, standard deviation etc.) using appropriate units of time. The duration of exposure to study drug will be categorized into time intervals; frequency counts and percentages of patients with exposure in each time interval will be presented. The derived parameters above will also be listed overall and by indication and formulation using Safety Set.

Dose Changes

The number and percentage of patients with dose interruption, reduction and increase will be summarized overall and by indication and formulation in the safety set. Dose interruption, reduction and increase are defined as follows:

- **Interruption** is defined as any period of zero total daily dose followed by a non-zero dose.
- **Reduction** is defined as any decrease from the immediate prior non-zero total daily dose. Zero daily doses are not regarded as reductions.
- **Increase** is defined as any increase from the immediate prior non-zero total daily dose.

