7.4.1 Adverse events (AEs)

Treatment emergent AEs are defined as those that started on or after the study medication, or those that started before study medication but worsened afterwards. AEs starting after 84 days following the last dose of pasireotide LAR treatment and after 30 days following the last dose of pasireotide s.c. treatment are not considered treatment emergent AEs. Summary tables for adverse events (AEs) have to include only AEs that started or worsened during the on-treatment period, the **treatment-emergent** AEs. However, all safety data

(including those from the post-treatment periods) will be listed and those collected during the post-treatment period are to be flagged.

The incidence of treatment-emergent adverse events (new or worsening from baseline) will be summarized by system organ class and/or preferred term, severity based on CTCAE grades (version 4.03), type of adverse event, relation to study treatment. The summary will include AEs regardless of study-drug relationship. The same analysis will be repeated for SAEs.

All treatment emergent AEs and SAEs will be listed. In this listing, the information on the relationship to study treatment will be included.

Adverse events will be coded using the Medical dictionary for regulatory activities (MedDRA) terminology using the latest available MedDRA version at the time of the analyses and the information of MedDRA version will be specified in the footnote of relevant outputs.

The following selection of AEs will be listed and summarized separately using Safety Set. AEs will be summarized for all grades and for grade 3 or 4 side-by-side.

- AEs
- SAEs
- AEs leading to study drug discontinuation
- AEs requiring dose adjustment or interruption
- AEs requiring additional therapy
- Adverse events of special interest (AESI)

For the legal requirements of ClinicalTrials.gov and EudraCT, two required tables on treatment- emergent adverse events which are not serious adverse events with an incidence greater than 5% and on treatment-emergent serious adverse events and SAE suspected to be related to study treatment will be provided by system organ class and preferred term on the safety set population.

If for a same patient, several consecutive AEs (irrespective of study treatment causality, seriousness and severity) occurred with the same SOC and PT:

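### AE, SAE and AESI tables give only counts and percentages although follow-up differs between patients by design, so they mix risk with length of observation and show no pattern over time

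*SAP*

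**What the plan says.** SAP 7.1.1 defines the primary assessment: "The assessment of safety will be based mainly on the frequency and severity of AEs, AESI and SAEs". SAP 7.1.2 makes it descriptive, overall and by indication and formulation, with no hypothesis. SAP 7.4.1 states the measure: "The incidence of treatment-emergent adverse events (new or worsening from baseline) will be summarized by system organ class and/or preferred term". The same is repeated for SAEs, and AESIs are summarised as one of several AE selections. The general rule in SAP 4.1 is that "qualitative data will be described using frequency and percentages". The 5% threshold for the registry tables in SAP 7.4.1 confirms that incidence there means a percentage of patients. The denominator in SAP 6.2.2 is "all patients who received at least one dose of study medication (Pasireotide) after enrolling into the roll-over protocol".

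On follow-up, SAP 2.4 sets a common calendar end: "End of study is defined as either 10 years from FPFV (or until 10-Jun-2023 in the UK", or earlier if all patients have left. Protocol 4.1 keeps treatment open-ended for each patient. Protocol 7.1.5.1 provides for exit when the drug is reimbursed in the patient's indication or available through a country programme. The on-treatment period in SAP 4.1 runs from the first roll-over dose "to 3 months (84 days) following the last dose of pasireotide LAR treatment and to 1 month (30 days" after the last s.c. dose.

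SAP 7.3 derives duration of exposure per patient and summarises it by indication and formulation, both as a continuous measure and in time categories. Neither protocol section 10 nor the SAP uses it as a denominator for adverse events, and neither plans time to first event, cumulative incidence, or AE tables by time since roll-over.

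**The concern.** A percentage of patients with an event is easy to read when everyone is observed for about the same time. Here one roll-over dose puts a patient in the denominator, and another patient may contribute most of a decade. The percentage then depends on how long patients were watched as well as on how often events occur.

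Two things are at stake. First, percentages for indication or formulation groups with different follow-up are hard to set against each other. Second, a cumulative percentage does not show whether events cluster soon after roll-over or continue at a steady rate, and that is a central question for a long-term safety objective. Since the study is purely descriptive, these tables are its main result.

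**Working it through.** **No figure to reproduce.** Protocol 10.7 and 10.8 give no sample size or power, and no event rate is stated. The rates below are assumptions.

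**Is follow-up unequal?** The enrolment counts come from the amendment rationales and are used only as facts about accrual.
- Amendment 1 (undated in the text): "This roll-over study has been opened since 10-Jun-2013 currently with a total of 95 patients enrolled and 80 patients ongoing". Amendment 2 (29-Sep-2017): 301 enrolled, 259 ongoing.
- Entered between the two counts: 301 − 95 = 206, and 206/301 = 68%.
- No longer ongoing at Amendment 2: 301 − 259 = 42, and 42/301 = 14%. From 10-Jun-2013 to 29-Sep-2017 is 4.3 years, so these 42 had at most about that long.
- Longest possible follow-up to 10-Jun-2023 (the UK end date, with the opening date taken as first patient first visit): 10.0 years for entry on 10-Jun-2013 and 5.69 years for entry on 29-Sep-2017.

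**Effect on a crude percentage.** With a constant hazard h and no early exit, P = 1 − exp(−hT).

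| h per 100 patient-years | P at 5.69 y | P at 10.0 y | Ratio |
|---|---|---|---|
| 2 | 10.8% | 18.1% | 1.7 |
| 5 | 24.8% | 39.3% | 1.6 |
| 10 | 43.4% | 63.2% | 1.5 |

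The risk per year is identical within each row.

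**Can the SAP 7.3 exposure table repair this?** Partly. Dividing patients with an event by full exposure (P/T) gives, per 100 patient-years:
- h = 2: 1.89 versus 1.81 (gap 4%)
- h = 5: 4.35 versus 3.93 (gap 11%)
- h = 10: 7.62 versus 6.32 (gap 21%)

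The remaining gap arises because exposure does not stop at the first event. The exposure clock also stops before the treatment-emergent window closes. For s.c. it ends at the last dose, so the shortfall is 30 days. For LAR it ends at "min(last date of rollover study drug+27, date of death, date of data cut-off"), so the shortfall is 84 − 27 = 57 days. The relative LAR/s.c. error is (1 + 57/365.25)/(1 + 30/365.25) − 1 = 6.8% at 1 year of exposure and 1.5% at 5 years, which is minor at long follow-up.

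**Pattern over time.** Take a hazard of 0.30 in year 1 and 0.02 a year afterwards. The cumulative hazard at 10 years is 0.30 + 9 × 0.02 = 0.48, so P = 38.1%. A constant 0.048 a year gives the same 38.1%. Year-1 risk is 25.9% in the first case and 4.7% in the second, and a cumulative percentage cannot tell them apart.

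**Limit of a single overall rate.** With that same early hazard, time at risk is (1 − e^−0.30)/0.30 = 0.864 years in year 1, plus e^−0.30 × (1 − e^(−0.02(T−1)))/0.02 afterwards.
- T = 5.69: P = 32.6%, time at risk 0.864 + 3.316 = 4.180 years, rate 7.8 per 100 patient-years.
- T = 10.0: P = 38.1%, time at risk 0.864 + 6.102 = 6.966 years, rate 5.5 per 100 patient-years.

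An overall first-event rate is therefore free of the follow-up effect only when the hazard is roughly constant, and rates by interval are needed as well.

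**The case against.** The strongest reply is that this is a single-arm access study. Protocol 2.2 plans no formal analysis, the endpoint is frequency and severity, and n (%) delivers that. The reply is right that no error rate or sample size is affected. It does not settle the matter, because a rate with a confidence interval is equally descriptive and answers the stated objective better.

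Second, the plan already shows much of what is needed. SAP 7.3 tabulates exposure in time categories for the same groups, and doses and AEs are listed. A reader can see the spread of follow-up, and rates could be derived later. This stands and lowers the weight of the point. What remains is that later derivation would rest on choices the SAP leaves open, such as how to treat patients who receive both formulations, which Protocol 5.2 allows.

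Third, a reader might infer that the tables set indication and formulation columns next to each other and that the contrast is out by about 1.6-fold. The documents support neither. SAP 7.4.1 describes a side-by-side layout only for all grades against grade 3 or 4. The 5.7 and 10.0 years are entry-date extremes among the first 301 patients, not the follow-up of any group; later entry and earlier exit are both possible. Indication groups also differ in disease and parent-study selection, so person-time rates would not by themselves make them comparable.

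**Conclusion.** The concern holds as a limit on what the planned tables can say. TEAEs, SAEs and AESIs are summarised only as counts and percentages over unequal observation, with no link to exposure and no view by time since roll-over. The omission and the unequal follow-up are clear from the text. The size of the consequence is not: 24.8% versus 39.3% rests on an assumed constant hazard and two hypothetical entry dates with no early exit. Actual follow-up by group is not in the documents, so no claim can be made about how far, or in which direction, any planned column is distorted. The change should be made before database lock, but nothing in the study's validity depends on it.

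**What to change.** Keep the crude n (%). In SAP 7.4.1 add:

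1. For TEAEs overall, SAEs and each AESI category: patients with a first event per 100 patient-years at risk, with 95% CI, overall and by indication and formulation. Time at risk runs from the first roll-over dose to the earliest of first event, end of the on-treatment period, death or cut-off.
2. One stated rule that assigns person-time and events for patients who receive both formulations, so that no person-day is counted twice.
3. For SAEs and AESI categories: the same rates by time since first roll-over dose (for example 0–1, 1–2, 2–5 and >5 years), with patient-years at risk in each interval.
4. A label stating that the results are descriptive and refer to roll-over time in a selected population, not to total pasireotide exposure. Patients came from parent studies, and those permanently discontinued there were excluded (Protocol 5.3).

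Record the addition in SAP section 3, as part of the descriptive primary summary. The dose, AE, death and cut-off dates needed are already collected. The cost is SAP wording, programming to split person-time, and a larger table set.

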7.4.2 Deaths

Separate summaries for on-treatment death and all deaths (including on-treatment and post- treatment) will be produced by primary system organ class and preferred term overall and by indication and formulation using the Safety Set. On-treatment and all

deaths will be listed overall and by indication and formulation and post treatment deaths will be flagged.

8 ATTACHMENTS

8.1 MAIN PROTOCOL DEVIATION LIST

Protocol Deviation Category	Description
Eligibility and Entry Criteria*	I01 Patient is not currently enrolled in a Novartis sponsored study receiving pasireotide and has not fulfilled all their requirements in the parent study
Eligibility and Entry Criteria*	I02 Patient is not currently benefiting from the treatment with pasireotide
Eligibility and Entry Criteria*	I03 Patient has demonstrated non- compliance, as assessed by the investigator, with the parent study protocol requirements
Eligibility and Entry Criteria*	I04 Patient is unwilling and/or not able to comply with scheduled visits, treatment plans and any other study procedures
Informed Consent Criteria*	105 Informed consent not signed at all.
Informed Consent Criteria*	I06 ICF not signed before patient received study drug
Eligibility and Entry Criteria*	E01 Patients terminated from the parent protocol and is not eligible to participate in the study.
Eligibility and Entry Criteria*	E02 Patient receiving pasirectide in combination with unapproved or experimental treatments
Eligibility and Entry Criteria*	E03 Sexually active male patient not using highly effective contraception
Eligibility and Entry Criteria*	E04 Pregnant or nursing (lactating) women enrolled into the study but did not receive study drug
Eligibility and Entry Criteria*	E05 Women of childbearing potential, not using highly Effective methods of contraception.
Eligibility and Entry Criteria*	E06 Patient is pregnant at study entry (first dose study drug was administered)
Study Procedures Criteria*	D01 Patient met hepatic discontinuation criteria and not withdrawn
Study Procedures Criteria*	D02 Patient met QT discontinuation criteria and not withdrawn
Study Procedures Criteria*	D03 Patient met hyperglycemic Discontinuation criteria and not withdrawn

Study Procedures Criteria*	D04 Patient became pregnant during the study and was not withdrawn
Study Procedures Criteria*	D05 Investigator determines that patient is no longer benefiting from treatment but did not discontinue patient from study
Study Procedures Criteria*	Other Criteria for premature patient withdrawal was met and not withdrawn
Investigation Product (IP) Compliance*	S01 Missed injection of study medication
Investigation Product (IP) Compliance*	S02 Starting dose of pasireotide differs from last dose received in the parent study
Investigation Product (IP) Compliance*	S03 Parent protocol medication taken instead of CSOM230B2412 medication at visit 1
Investigation Product (IP) Compliance*	S04 Dose up/down titration not done as defined in parent protocol
Investigation Product (IP) Compliance	Time window between administration of pasireotide LAR/s.c. not according to the protocol (LAR 28 days ± 7 days / s.c. 84 days ± 14 days from the IP administration date).
Investigation Product (IP) Compliance	Pharmaceutical formulation not administered as defined in the parent protocol
Investigation Product (IP) Compliance*	S06 Time window between administration of pasireotide LAR too short or too long (less than 14 days and more than 56 days from the last monthly injection).
Investigation Product (IP) Compliance	Patient was mistakenly provided Novartis labelled IP
Investigation Product (IP) Compliance	Patient was mistakenly provided expired IP
Investigation Product (IP) Compliance	Due to delays in obtaining regulatory approvals for sponsor change and due to unavailability of the Novartis labelled IP, Recordati labelled IP was used
Investigation Product (IP) Compliance	IP kit discarded by the site staff by mistake
Concomitant Medication Criteria*	M01 Patient took an excluded concomitant Medication
Study Procedures Criteria	IP storage temperature out of range.
Study Procedures Criteria	IP Temperature log is not available at site for a certain period
Informed Consent Criteria*	G01 Informed consent not Appropriately obtained (e.g. Incorrect version signed, new ICF version approved not signed on a consecutive visit, site personnel not delegated signed the ICF, etc.,)
Informed Consent Criteria	Other general ICF documentation errors (e.g. incomplete name/signature, boxes not checked where needed, missing initials on any ICF page where needed, etc.).

Source Document Criteria*	G02 Source Documentation lost
Administrative Criteria*	G03 Study drug administration not properly documented in CRF and drug accountability logs
Serious Adverse Event Criteria*	G04 SAE not reported within 24 hours of learning of its occurrence
Study Procedures Criteria*	G06 Male patient is sexually active and does not use condoms during the study and for 1 months after pasireotide s.c. last dose and 3 months after pasireotide LAR last dose and should not father a child in this period.
Study Procedures Criteria*	G07 Investigator failed to question patient on any possible adverse events and serious adverse events
Study Procedures Criteria*	G08 Investigator failed to assess if the patient was continuing to receive clinical benefit at the visit.
Study Procedures Criteria	Investigator failed to document in eCRF if the patient was continuing to receive clinical benefit at the visit
Visit Schedule Criteria*	G10 Missed visit due to COVID-19
Visit Schedule Criteria*	G11 Visit done outside of study site due to COVID-19
Study Procedures Criteria*	G12 Assessment/ procedure changed due to COVID-19
Study Procedures Criteria*	G13 Drug supply method changed due to COVID-19
Investigation Product (IP) Compliance*	G14 Treatment not given due to COVID-19
Other Criteria*	G15 Discontinuation due to COVID-19
Study Procedures Criteria*	G16 Patient failed to adhere to protocol requirements or visit schedule
Study Procedures Criteria*	G17 Female patient of childbearing potential did not complete diary with dates and outcome of at-home urine pregnancy tests while on study treatment
Study Procedures Criteria	Site staff are allowed to work for limited hours due to Covid 19 restrictions

Category	Adverse Event Term
AESI Bradycardia related AEs	Atrial conduction time prolongation (PT)
	Atrioventricular block (PT)
	Atrioventricular block complete (PT)
	Atrioventricular block second degree (PT)
	Atrioventricular dissociation (PT)
	Bradycardia (PT)
	Central bradycardia (PT)
	Conduction disorder (PT)
	Defect conduction intraventricular (PT)
	Electrocardiogram PQ interval prolonged (PT)
	Electrocardiogram PR prolongation (PT)
	Electrocardiogram QRS complex prolonged (PT)
	Electrocardiogram QT prolonged (PT)
	Long QT syndrome (PT)
	Paroxysmal atrioventricular block (PT)
	Sinoatrial block (PT)
	Sinus bradycardia (PT)
AESI Coagulation related AEs	Blood fibrinogen decreased (PT)
	Blood thrombin decreased (PT)
	Blood thromboplastin abnormal (PT)
	Blood thromboplastin decreased (PT)
	Coagulation factor IX level decreased (PT)
	Coagulation factor V level decreased (PT)
	Coagulation factor VII level decreased (PT)
	Coagulation factor X level decreased (PT)
	Coagulation factor decreased (PT)
	Hypofibrinogenaemia (PT)
	International normalised ratio abnormal (PT)
	Prothrombin level decreased (PT)
	Prothrombin time prolonged (PT)
	Prothrombin time ratio decreased (PT)
	Thrombin time prolonged (PT)
AESI Gallbladder and biliary related AEs	Bile duct necrosis (PT)
	Bile duct obstruction (PT)
	Bile duct stenosis (PT)
	Bile duct stone (PT)

